- Viral load one day and one week after the last session
- Chest Xray changes one day and one week after the last session
- Percentage of patients with positive IgG serology one day and one week after the last session
- Percentage of patients with positive IgM serology one day and one week after the last session
- Pulmonary function test one day and one week after the last session
- Time to symptoms recovery
- Percentage of patients who required invasive intubation
- Time to recovery (negative PCR twice) – TTCR
- Mortality rate in 30 days
- Safety – percentage of adverse events

STUDY DESIGN

Subjects: Patients at Maimonides Medical Center (MMC)

Eligibility Criteria:

Patients who are (1) within 7 days of need of oxygen supply, (2) positive to SARS-CoV-2 through RT-PCR, (3) have at least one risk factor for bad prognosis of COVID-19: hypertension, diabetes mellitus, ischemic heart disease, smoking, age>50, etc., (4) have respiratory insufficiency: Room Air SpO₂ <94% or PaO₂/FiO₂<300mmHg, (5) are older than 18 years of age and (6) have ability to sign an informed consent will be included in the study.

Patients who are (1) negative to SARS-CoV-2 through RT-PCR, (2) have a HBOT contraindication: pneumothorax, pneumomediastinum, claustrophobia, ear/sinus disease which aren't allowed in HBOT, known chronic pulmonary disease: severe emphysema or known pulmonary bullae, (3) have pregnancy and/or (4) have inability to sign an informed consent will be excluded from study.

Design:

This study is a prospective randomized controlled, double blind clinical trial performed on laboratory confirmed COVID-19 infection admitted patients in MMC. It involves the use of MMC monoplace HBO chambers. The trial will include 30 patients who will undergo either hyperbaric oxygen therapy (HBOT) or Normobaric oxygen therapy (NBOT), randomized on a 2:1 ratio, within 4 days in addition to the standard treatment including oxygen, drugs, steroids, bronchodilators, antibiotics and others.

The evaluation procedure includes symptom monitoring, room air saturation, vital signs monitoring, pulmonary function and blood tests at baseline, one day and one week after the last session. In addition, one hour prior to and post session saturation and vitals will be monitored.

Data Collection Procedures:

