Upon signing an informed consent, the patients will be randomized 2:1 to hyperbaric oxygen therapy group (HBOT) and normobaric oxygen therapy group (NBOT) (Randomization will be performed using a computer software based on patient id). Following the randomization, the patients will undergo evaluation including symptoms, vitals, pulmonary function, blood tests.

The patients will undergo 8 sessions of either hyperbaric/normobaric oxygen therapy, 2 sessions per day, in 4 consecutive days. During the sessions, the symptoms and vitals will be monitored. 1 day and 1 week following the last session, reevaluation will be performed.

Protocol Day 1

1. Baseline evaluation: blood test including: arterial blood gases, 2 CBC tubes, 2 Gel tubes (10-15 cc total), vitals (temperature, blood pressure, heart rate, room air saturation), symptoms questionnaire, pulmonary function test.
2. Vitals (temperature, blood pressure, heartrate, room air saturation) one hour prior to session
3. One-hour session NBO/HBO
4. Vitals (temperature, blood pressure, heartrate, room air saturation) one hour after the session.
5. Vitals (temperature, blood pressure, heartrate, room air saturation) one hour before the 2nd session.
6. One-hour session NBO/HBO (8 hours following the first session)
7. Vitals (temperature, blood pressure, heartrate, room air saturation) one hour after the session.
8. Daily oxygen supply dose monitoring.

Protocol Day 2-4

1. Daily symptoms questionnaire
2. Vitals (temperature, blood pressure, heartrate, room air saturation) one hour prior to session
One-hour session NBO/HBO
3. Vitals (temperature, blood pressure, heartrate, room air saturation) one hour after the session.
4. Vitals (temperature, blood pressure, heartrate, room air saturation) one hour before the 2nd session.
5. One-hour session NBO/HBO (8 hours following the first session)
6. Vitals (temperature, blood pressure, heartrate, room air saturation) one hour after the session.
7. Daily oxygen supply dose monitoring.

Follow up Protocol

1. Repeat evaluations one day after the last session and one week after the last session:
 - Blood test including: arterial blood gases, 2 CBC tubes, 2 Gel tubes (10-15 cc total)
 - Vitals (temperature, blood pressure, heart rate, room air saturation)
 - Symptoms questionnaire
 - Pulmonary function test.
2. Oropharyngeal swab for SARS-CoV-2 RT-PCR every 3 days for 1 week
3. Clinical monitoring for 30 days

Data Analysis:

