Continuous data will be expressed as means \pm standard-deviations. Independent and dependent t-test with two-tail distribution will be performed to compare variables between and within the two groups, when a normality assumption holds according to Kolmogorov-Smirnov test. Categorical data will be expressed in numbers and percentages and compared by chi-square tests. Univariate analyses were performed using Chi-Square/Fisher's exact test to identify significant variables. A value of $p<0.05$ will be considered significant.

Data analysis will be performed with Matlab R2019b (Mathworks, Natick, MA) Statistics Toolbox.

Sample Size: 30

Based on a previous study on HBOT effect on ARDS [14], with 95% power and significance level of 5%, and a groups difference of 30 (SD 15-18) in the PaO₂/FiO₂ and a 2:1 groups allocation, the sample requires 7 NBOT patients and 13 HBOT patients. Considering 15% dropout, we will recruit 10 NBOT patients and 20 HBOT patients, 30 in total.

Expected Outcomes:

The primary outcomes measures that will be accessed in the study are:

- Oxygenation index = PaO₂/FiO₂ one day after the last session.
- SpO₂ – room air saturation one hour before and after a session, 6 hours after a session and one day after the last session.
- NES – Early warning score, before and after each session, 6 hours after each session and one day after the last session
- Inflammatory parameters one day after the last session: WBC, Immune profile, CRP, ESR, Procalcitonin, TNF α , IL1, IL2, IL6, IL10.

The secondary outcomes measures that will be accessed in the study are:

- Oxygenation index = PaO₂/FiO₂ one week after the last session.
- SpO₂ – room air saturation one week after the last session.
- NES – Early warning score, one week after the last session
- Inflammatory parameters one week after the last session: WBC, Immune profile, CRP, ESR, Procalcitonin, TNF α , IL1, IL2, IL6, IL10.
- Symptoms level one day and one week after the last session
- Viral load one day and one week after the last session
- Chest Xray changes one day and one week after the last session
- Percentage of patients with positive IgG serology one day and one week after the last session
- Percentage of patients with positive IgM serology one day and one week after the last session
- Pulmonary function test one day and one week after the last session
- Time to symptoms recovery
- Percentage of patients who required invasive intubation
- Time to recovery (negative PCR twice) – TT_{CR}

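### Baseline is taken after randomisation with no masking described, which leaves the within-group tests and any change-from-baseline comparison open to avoidable bias

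*Combined protocol and SAP*

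**What the plan says.** All references are to the combined protocol and SAP.

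- **Order of procedures (Study Design, Data Collection Procedures).** The section opens: "Upon signing an informed consent, the patients will be randomized 2:1 to hyperbaric oxygen therapy group (HBOT" (the sentence goes on to name the normobaric arm, NBOT). It continues: "Following the randomization, the patients will undergo evaluation including symptoms, vitals, pulmonary function, blood tests".
- **Status of that evaluation (Protocol Day 1, item 1).** The same tests are called the baseline: "Baseline evaluation: blood test including: arterial blood gases", followed by other bloods, vital signs, a symptoms questionnaire and a pulmonary function test. They come before the first session. No section schedules a study baseline before randomisation.
- **Blinding (Design).** "This study is a prospective randomized controlled, double blind clinical trial". No sham session, masking of patients or staff, or blinded assessor is described.
- **Allocation (Data Collection Procedures).** "Randomization will be performed using a computer software based on patient id". Nothing says when the arm is disclosed, or to whom.
- **Data held before enrolment (Eligibility Criteria).** Patients must "have respiratory insufficiency: Room Air SpO₂ <94% or PaO₂/FiO₂<300mmHg". Either measure suffices, and neither is designated as the study baseline.
- **Analysis (Data Analysis).** "Independent and dependent t-test with two-tail distribution will be performed to compare variables between and within the two groups". No change-score comparison between arms, baseline-adjusted model, analysis population or missing-data rule is given.

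**The concern.** A baseline recorded after allocation is protected only if nobody involved in measuring it knows the arm. Here the text offers the double-blind label and nothing that would put it into effect, in a trial comparing pressurised with unpressurised oxygen sessions.

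The baseline items are not equally vulnerable. The symptoms questionnaire is subjective and pulmonary function depends on effort; both could move with a patient's or assessor's expectations. The blood gas is harder to influence, but its timing and oxygen setting are not standardised in the text, so it is not wholly protected. Room-air saturation fixes the inspired oxygen by definition.

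Two things are at stake. First, a baseline shifted in one arm enters that arm's before-after difference in full. Second, a patient who withdraws between allocation and evaluation counts as randomised but has no study baseline. If the arm is known by then, such losses may differ by arm. Neither the interval nor the handling of such patients is specified.

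**Working it through.** **Inputs.** From Sample Size: PaO₂/FiO₂ difference 30, SD 15–18, 95% power, 5% significance, 2:1 allocation, 7 NBOT + 13 HBOT required, 10 + 20 = 30 recruited. From Data Analysis: two-tailed tests. The baseline shifts, the adjustment slope and the numbers lost below are assumptions, because the document gives none.

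**Step 1. The plan's own figure.** With the normal approximation and 2:1 allocation, the smaller arm needs

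n = (1 + 1/2) × (1.960 + 1.645)² × SD² / 30².

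| SD | n (formula) | Normal approximation | t-test (noncentral t) | Power at 7 + 13 |
|---|---|---|---|---|
| 15 | 4.87 | 5 + 10 | 6 + 12 | 0.981 |
| 16.5 | 5.90 | 6 + 12 | 7 + 14 | 0.956 |
| 18 | 7.02 | 8 + 16 | 8 + 16 | 0.919 |

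At the mid-range SD of 16.5 the t-test needs 21 patients against the stated 20, so the figure reproduces closely as an ordinary two-group comparison. No baseline value or before-after correlation enters it.

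**Step 2. Which analyses use the baseline.** Let the recorded baseline be shifted by s_H in HBOT and s_N in NBOT, with δ = s_H − s_N.

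| Analysis | In the plan? | Effect of the shift |
|---|---|---|
| Between-group t-test of the day-after value | Yes | None |
| Within-group (dependent) t-test from baseline | Yes, though the paired time points are not named | That arm's mean change is off by its own shift |
| Between-group comparison of change scores | Not named, not excluded | Estimate off by δ |
| Baseline-adjusted comparison | Not named | Estimate off by slope × δ |

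The within-group tests do not themselves estimate HBOT against NBOT, but they are planned and they need a before value.

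**Step 3. Size if change scores were used.**

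- δ = 3: 3/30 = 10% of the design difference.
- δ = 5: 5/30 = 17%.
- δ = 10: 10/30 = 33%.

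With an assumed slope of 0.5, an adjusted analysis would carry 0.5 × 5 = 2.5 to 0.5 × 10 = 5 mmHg. The direction is unknown: a baseline recorded relatively low in HBOT would inflate the apparent benefit, and one recorded relatively high would shrink it.

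**Step 4. Missing baselines.** One patient is 1/10 = 10% of the NBOT arm or 1/20 = 5% of the HBOT arm. For an analysis that drops patients without a baseline, with a difference of 30 and the allocation kept near 2:1:

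| Lost of 30 | Split | Power, SD 15 | Power, SD 18 |
|---|---|---|---|
| 0 | 10 + 20 | 0.999 | 0.986 |
| 2 | 9 + 19 | 0.997 | 0.977 |
| 5 | 8 + 17 | 0.994 | 0.961 |
| 10 | 7 + 13 | 0.981 | 0.919 |

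The last row is simply the plan's own minimum sample. The issue is therefore bias and incomplete data, not power.

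**The case against.** The strongest reply is that the trial is declared double blind. If blinding is effective, the order of randomisation and baseline cannot matter through knowledge of the arm. The text does not say that anyone is told the allocation before baseline, and the end of Adverse Event Reporting refers to an overall-study protocol that is not supplied and might describe masking. This stands as a condition: the bias is possible, not shown. It does not settle the matter, because the label is unsupported by any procedure in this document.

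A reader might infer that the primary PaO₂/FiO₂ comparison is biased. The document does not support that. Study Objectives and Expected Outcomes define this outcome as the value on the day after treatment ends, not a change, and an independent t-test of it uses no baseline.

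A reader might also infer that a patient lost early has no baseline data at all. That is too strong. An SpO₂ or PaO₂/FiO₂ value must exist for eligibility. Baseline is the first item on Day 1 in patients already in hospital, and someone who withdraws before it would usually lack outcomes too. What stands is narrower: the eligibility value may be only one of the two measures, it is not designated as baseline, and it includes no symptoms or pulmonary function.

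Finally, if masking is absent, assessments after treatment are exposed as well, and that is the larger problem. This is correct, and reordering does not touch it.

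**Conclusion.** The point holds as a minor design improvement. The stated order is clear and uncontradicted, and it exposes the dependent t-tests and any change-from-baseline comparison to a risk that can be removed at almost no cost. The risk is greatest for symptoms and pulmonary function, which are secondary outcomes, and smaller for the blood gas.

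The size is unknown. The 17% to 33% figure is arithmetic on an assumed differential shift of 5 to 10 mmHg and applies only if PaO₂/FiO₂ is analysed as a change score, which the plan neither names nor rules out. The conclusion also assumes that the arm may be known when baseline is taken; effective masking described elsewhere would remove that part and leave only the patients without a study baseline. Nothing here shows that the planned day-after PaO₂/FiO₂ comparison is biased or that the sample size is inadequate.

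**What to change.** Replace the sequence in Data Collection Procedures with wording such as: *After informed consent, patients complete the baseline evaluation (symptoms, vital signs, pulmonary function, blood tests including arterial blood gases). Once it is recorded, the patient is randomised 2:1, the allocation is released, and the first session follows.* Align Protocol Day 1 with this order.

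Add one sentence on how a randomised patient without a baseline is handled. Confirm also that the arm cannot be worked out in advance from the patient identifier, since reordering protects baseline only if the allocation is unknown until then.

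The cost is wording. The same tests are done before the first session, and the sample size stays at 30. The change does not mask the readings taken around each session or the assessments after treatment; those need a separate description of blinding.

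### The one-day and one-week reevaluations are timed from the last session, with no study day, window or rule for patients who receive fewer than 8 sessions

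*Combined protocol and SAP*

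**What the plan says.** In Data Collection Procedures (Study Design), treatment is 8 sessions, "2 sessions per day, in 4 consecutive days", and then "1 day and 1 week following the last session, reevaluation will be performed". The Follow up Protocol repeats this timing for arterial blood gases, the other blood tests, vitals, symptoms and pulmonary function. The outcome lists in Study Objectives and Expected Outcomes use it too.

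The Data Analysis section compares the arms without adjustment: "Independent and dependent t-test with two-tail distribution will be performed to compare variables between and within the two groups". Categorical outcomes get chi-square or Fisher's exact tests.

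Patients who do not finish appear only in the sample size paragraph ("Considering 15% dropout"). The documents number the treatment days 1 to 4 but give no day number or window for the two reevaluations. They do not say what the last session is for a patient who stops early or receives none, whether such a patient is assessed, or which patients are analysed.

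**The concern.** The number of sessions received is settled after randomisation and may depend on the arm. A patient may stop because the chamber is not tolerated, because of deterioration, or because of recovery. If the assessment date follows the last session actually received, that same event decides when the outcome is measured.

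The introduction describes COVID-19 ARDS as rapidly progressive, and the plan measures the same markers at one day and again at one week, so it treats them as changing over days. A day-2 value from one patient and a day-5 value from another are then not the same outcome. If one arm has more early stopping, part of the difference between arms is a difference in time, and nothing in the planned tests removes it. For PaO2/FiO2, the variable that sets the sample size, this reading is the only primary time point.

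**Working it through.** **1. The plan's own figure.** From the Sample Size section: difference 30 in PaO2/FiO2, SD 15 to 18, 5% significance, 95% power, 2:1 allocation, and "the sample requires 7 NBOT patients and 13 HBOT patients". The two-sided test comes from Data Analysis. The standard error of the difference is SD × √(1/7 + 1/13) = 0.469 × SD, which is 7.0 at SD 15 and 8.4 at SD 18. Noncentral-t power on 18 degrees of freedom is 98.1% at SD 15, 95.6% at SD 16.5 and 91.9% at SD 18. The stated size therefore reproduces at a mid-range SD. It does not depend on visit timing; the difference of 30 serves below only as a yardstick.

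**2. Visit days under the literal reading.** With two sessions a day, session k falls on day k/2, rounded up. Add 1 or 7 days.

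| Last session received | Study day | One-day visit | One-week visit | Days sooner than planned |
|---|---|---|---|---|
| 1 or 2 | 1 | day 2 | day 8 | 3 |
| 3 or 4 | 2 | day 3 | day 9 | 2 |
| 5 or 6 | 3 | day 4 | day 10 | 1 |
| 7 or 8 | 4 | day 5 | day 11 | 0 |

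Missing only session 8 changes nothing. A patient with no session has no visit date.

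**3. Reach.** All four primary outcomes include the reading one day after the last session. For PaO2/FiO2 and the inflammatory parameters it is the only primary time point. SpO2 and NES also have readings around each session, which are not affected. Of 15 secondary outcomes, 10 use this timing. The other five do not: time to symptom recovery, intubation, time to PCR recovery, 30-day mortality and adverse events.

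**4. Possible size (illustration only).** Shift in the arm difference = excess share stopping early in one arm × days early × change in PaO2/FiO2 per day. The documents give none of these three inputs. Assume an excess of 15 percentage points (3 of 20 HBOT patients, if HBOT is the arm affected):

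| Days early | 5 mmHg/day | 10 mmHg/day | 15 mmHg/day | 20 mmHg/day |
|---|---|---|---|---|
| 2 | 1.5 | 3.0 | 4.5 | 6.0 |
| 3 | 2.25 | 4.5 | 6.75 | 9.0 |

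Over 5 to 15 mmHg per day this is 1.5/30 = 5% to 6.75/30 = 22.5% of the design difference. At 20 mmHg per day and 3 days it is 9/30 = 30%. Doubling the excess to 30 points doubles every entry. With equal stopping and equal daily change in both arms, the shift is 0. The sign depends on which arm stops more and on whether PaO2/FiO2 is rising or falling.

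**5. Against sampling error.** With all 10 and 20 patients, the standard error is SD × √(1/10 + 1/20) = 0.387 × SD, or 5.8 to 7.0. The range 1.5 to 6.75 reaches about one standard error only at its upper end.

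**The case against.** The strongest reply is that the course is fixed at 8 sessions laid out by protocol day, so the last session may simply mean the scheduled eighth. On that reading the visits already fall on days 5 and 11 for everyone. The text permits this reading but does not state it, so a reader who concludes that early stoppers will in fact be measured on day 2 goes further than the documents do.

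Second, patients who stop may be counted within the 15% dropout allowance and never reevaluated. The problem is then missing data and the choice of analysis population rather than mistimed values. That is also open, and is no better for the comparison.

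Third, no input to the illustration comes from the plan. The 15% is an overall dropout allowance, not a between-arm excess in early stopping. This stands: a reader might infer a demonstrated bias for or against HBOT, and the documents support neither its existence nor its direction.

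Fourth, not every outcome is affected. The per-session SpO2 and NES readings and five secondary outcomes keep their timing, and swabs every 3 days for a week give some virological data outside the two visits. This stands too, and the point is limited accordingly.

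**Conclusion.** The point holds as a gap in a stated timing rule. Followed literally, the rule lets the number of sessions received set the assessment day for PaO2/FiO2, the inflammatory parameters, the final SpO2 and NES readings and 10 of 15 secondary outcomes. The spread is up to 3 days (day 2 to 5, and day 8 to 11), and the planned tests do not correct for it.

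Whether this biases the comparison depends on three things the documents do not give: whether early stoppers are assessed and analysed, whether stopping differs by arm, and how fast the outcomes change. The 1.5 to 6.8 mmHg figure is conditional on the assumed inputs and does not estimate the bias in this trial. Patients who finish on schedule are unaffected. The change is worth making because it costs little, not because harm has been shown.

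**What to change.** Define day 1 as the day of the scheduled first session, so that a patient who receives no session also has a time origin. Then state in Data Collection Procedures and the Follow up Protocol, for example:

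*Reevaluation is performed on day 5 and on day 11, counted from the scheduled first session, within a stated window, in every randomised patient whatever number of sessions was received.*

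The sponsor should choose a short window that allows for delayed sessions. Replace the last-session timing by day 5 and day 11 in the outcome lists of Study Objectives and Expected Outcomes. Treatment, sample size and number of visits do not change.

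Patients who complete on schedule keep the same dates. Early stoppers have to be followed to the fixed days. A patient whose sessions are delayed may be assessed sooner after the final session or, if the delay exceeds the window, before it. The change does not deal with values missing through death or withdrawal.

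### Time to recovery (TTCR) and time to symptoms recovery have no time-to-event method, time origin or censoring rule, and no stated method can give a time to patients who have not recovered

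*Combined protocol and SAP*

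**What the plan says.** Study Objectives and Expected Outcomes both list "Time to recovery (negative PCR twice" (TTCR) and "Time to symptoms recovery" as secondary outcomes. Neither place gives a time origin, says whether the two negatives must be consecutive or which of them dates the event, or defines symptom recovery.

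Follow up Protocol lists PCR sampling once: "Oropharyngeal swab for SARS-CoV-2 RT-PCR every 3 days for 1 week". The first swab day is not stated. The 30-day follow-up is described only as clinical monitoring. A separate secondary outcome is "Viral load one day and one week after the last session", with no swab of its own listed.

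Symptom questionnaires fall at baseline and daily on days 2-4, then one day and one week after the last session (about study days 5 and 11).

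Data Analysis starts with "Continuous data will be expressed as means" with SDs. It then gives t-tests "when a normality assumption holds according to Kolmogorov-Smirnov test", with no alternative if normality is rejected. Categorical data are compared by chi-square, and a further sentence names "Chi-Square/Fisher's exact test to identify significant variables". No outcome is assigned to a test by name. Thirty-day mortality is a listed outcome, so deaths are anticipated.

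**The concern.** A time outcome with short follow-up has patients whose event is not seen. A t-test needs a number for every patient, and nothing in the plan supplies one for a patient who has not cleared by the last swab or who dies. What remains is a comparison of those who cleared, a subset formed after randomisation. If treatment speeds clearance, the effect shows mainly in how many patients clear within the week, and the mean time among clearers discards exactly that.

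The sparse schedule adds a second problem. With so few possible event days the recorded times are nearly constant, so the t-test may not be computable or may fail the normality condition. The plan then names nothing else for a time outcome. Origin, handling of non-clearers and choice of test would all be settled after the data are seen.

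**Working it through.** The plan gives no figure for TTCR. Its only calculation is the sample size for PaO₂/FiO₂, which does not bear on this point.

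**1. Possible event days.** Sampling every 3 days for a week gives two or three swabs. In days after the last session, the second negative can fall on:
- swabs 1/4/7 (the three-day schedule that also meets both viral-load days): day 4 or 7
- swabs 0/3/6: day 3 or 6
- swabs 3/6: day 6 only
- swabs 2/5: day 5 only

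**2. Assumptions.** The documents give no clearance rate, so this is an illustration:
- 20 HBOT v 10 NBOT patients (from Sample Size)
- exponential clearance with medians 5 v 10 days, P(cleared by t) = 1 − 2^(−t/median)
- error-free PCR and no deaths
- a second negative at a swab requires clearance by the swab before it
- clearance accrues either from the last session or from randomisation, with the last session taken as 4 days after randomisation

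**3. Worked case, swabs 1/4/7, clearance from the last session.**
- HBOT with a time: 1 − 2^(−4/5) = 0.426. Of these, those with a time of day 4: 1 − 2^(−1/5) = 0.129. Mean = 7 − 3 × 0.129/0.426 = 6.09 days.
- NBOT with a time: 1 − 2^(−4/10) = 0.242. Day 4: 1 − 2^(−1/10) = 0.067. Mean = 7 − 3 × 0.067/0.242 = 6.17 days.

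**4. All schedules** (HBOT v NBOT; times in days after the last session):

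| Swabs | Clearance from | With a time | Mean time | Fisher power | Log-rank power |
|---|---|---|---|---|---|
| 1/4/7 | last session | .426 v .242 | 6.09 v 6.17 | .112 | .134 |
| 1/4/7 | randomisation | .670 v .426 | 4.76 v 4.94 | .183 | .241 |
| 0/3/6 | last session | .340 v .188 | 6.00 v 6.00 | .077 | .107 |
| 0/3/6 | randomisation | .621 v .384 | 3.94 v 4.11 | .154 | .216 |
| 3/6 | last session | .340 v .188 | 6 v 6 | .077 | .107 |
| 3/6 | randomisation | .621 v .384 | 6 v 6 | .154 | .241 |
| 2/5 | last session | .242 v .129 | 5 v 5 | .028 | .053 |
| 2/5 | randomisation | .565 v .340 | 5 v 5 | .134 | .217 |

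Fisher power is by exact enumeration and log-rank power by simulation. The largest mean difference is 0.17 days. At medians 5 v 15 it is 0.24 days, and at 3.3 v 10 it is 0.33 days.

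**5. Is the t-test reached?** With two swabs, or with 0/3/6 and clearance from the last session, all times are equal and no t-test exists. For 1/4/7 from the last session, 20,000 simulated trials gave at least one arm with fewer than two times or no spread in 61%. Both arms passed K-S (using the estimated mean and SD) in about 21%, or 1% with the Lilliefors correction. With clearance from randomisation the uncorrected pass rate was about 5-6% (1/4/7) or 15-16% (0/3/6). These rates depend on how K-S is coded.

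**6. A different time origin.** Eligibility requires patients to be "within 7 days of need of oxygen supply". If TTCR were timed from that need, assumed uniform over 0-7 days before randomisation, the times spread out. For 1/4/7 with clearance from the last session, the NBOT mean is 6.17 + 4 + 3.5 = 13.67 days and the HBOT mean is 6.09 + 4 + 3.5 = 13.59 days, with SD 2.4 in each arm. The t-test is then easier to reach, but the share with a time is still 43% v 24% and the means still nearly coincide.

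**7. Precision of the proportion.** For 1/4/7 from the last session, the 95% CI half-width is 1.96 × √(.426 × .574/20 + .242 × .758/10) = 0.34. Over all rows it is 28 to 37 percentage points.

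**The case against.** A reader might infer that the plan excludes non-clearers and deaths, or that it will produce a biased t-test. The documents support neither. TTCR is not assigned to the t-test, and no exclusion is stated. Step 5 shows that on a last-session or randomisation origin the test is seldom reached, so the usual result is that no test is specified. That stands, and it is why the point is worded as a missing method. It does not rescue the plan: any mean that is reported still covers clearers only.

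The count of two or three swabs is also less firm than it looks. Viral load might be measured on separate PCRs, giving up to five time points, and the end of Adverse Event Reporting refers to an overall-study protocol that is not available here and may hold swab days or definitions. Extra PCRs would add possible event days, but all within about a week, so patients not cleared by then would still have no time.

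Some of the lost signal appears elsewhere: one-week viral load compares the arms without requiring clearance, and mortality is its own outcome. So a difference hidden in mean TTCR need not vanish from the trial. This limits the harm but does not make TTCR analysable.

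Finally, the 43% v 24% case assumes that clearance starts only at the last session. From randomisation it is 67% v 43%. The full range should be read, not one row.

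**Conclusion.** The concern holds as a gap in the analysis plan. Two listed time outcomes have no time-to-event method, origin or censoring rule, and none of the named methods can use a time for a patient who does not recover within follow-up. Under the assumed medians of 5 v 10 days, 24-67% v 13-43% of patients would have a TTCR while mean times differ by 0 to 0.17 days, so a halved median almost disappears from the mean. Often no t-test would be possible at all. These figures rest on assumed clearance rates, error-free PCR and no deaths. No size is given for time to symptoms recovery, which shares the gap in specification but is assessed on different days.

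The issue affects one or two of 15 listed secondary outcomes. The primary endpoints do not have the non-clearer problem, and the sample size is untouched. The missing fallback when K-S rejects normality is a general gap that also covers the continuous primary outcomes. The change should be made, but the trial's main conclusion does not depend on it.

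**What to change.** In Data Analysis, analyse TTCR and time to symptoms recovery in all randomised patients, timed from randomisation, with Kaplan-Meier and log-rank. Censor patients without the event at the last scheduled assessment, and keep deaths in the analysis as not recovered up to that time.

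Alongside TTCR, report the proportion of all randomised patients with two negative PCRs by the last scheduled swab. Count deaths and missing swabs as not cleared, use Fisher's exact test (already named) with a 95% CI for the difference, and add a sensitivity analysis counting missing swabs as cleared. This supplements the listed time outcome and does not replace it.

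In Follow up Protocol, state the swab days, whether viral load uses the same swabs, and whether the two negatives must be consecutive. Define symptom recovery, and say whether the 30-day clinical monitoring records symptoms. If it does, the last symptom assessment is day 30; if not, it is one week after the last session.

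Cost: no new visits, swabs or patients, only a few sentences and a little extra analysis. Power remains low at 30 patients: for 5 v 10 days, about 3-18% with Fisher and 5-24% with log-rank. The gain is a comparison that keeps every randomised patient and is fixed before the data are seen.
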